6.0 ENDPOINT ASSESSMENT

6.1 Definitions

For the purposes of this study, patients should be re-evaluated for response every 12 weeks (± 1 week). In addition to a baseline scan, confirmatory scans should also be obtained 8 weeks following initial documentation of objective response greater than Stable Disease (SD). Tumor assessments for all subjects should continue as per protocol even if dosing is interrupted. Tumor measurements should be made by the same investigator or radiologist for each assessment whenever possible. Changes in tumor measurements and tumor responses to guide ongoing study treatment decisions will be assessed by the investigator using RECIST.

Response and progression will be evaluated in this study using the new international criteria proposed by the revised Response Evaluation Criteria in Solid Tumors (RECIST) guideline (version 1.1)⁴⁶. Changes in the largest diameter (unidimensional measurement) of the tumor lesions and the shortest diameter in the case of malignant lymph nodes are used in the RECIST criteria.

High resolution CT with oral/intravenous contrast or contrast-enhanced MRI is the preferred imaging modalities for assessing radiographic tumor response. If a subject has a known allergy to contrast material, please use local prophylaxis standards to obtain the assessment with contrast if at all possible, or use the alternate modality. In cases where contrast is strictly contraindicated, a non-contrast scan will suffice. Screening assessments should be performed within 28 days of registration. Brain MRI is the preferred imaging method for evaluating CNS metastasis, and assessment is required during screening in all eligible subjects. All known or suspected sites of disease (including CNS if history of CNS metastases) should be assessed at screening and at subsequent assessments using the same imaging method and technique. If more than one method is used at screening, then the most accurate method according to RECIST 1.1 should be used when recording data, and should again be used for all subsequent assessments. Previously treated CNS metastases are not considered measurable lesions for purposes of RECIST determined response. Subjects with a history of brain metastasis should have surveillance MRI approximately every 12 weeks, or sooner if clinically indicated.

6.2 Primary Endpoint

Progression free survival defined as time in months from the date of first study treatment to the date of disease progression or death from any cause, whichever comes first. All patients who receive at least one dose of nivolumab/ipilimumab combination will be included in the primary analyses of PFS. The Response Evaluation Criteria in Solid Tumors (RECIST 1.1) criteria will be used for objective tumor response assessment (when disease is measurable and non-measurable).⁴⁶

- Patients with IBC often do not have measurable disease. For example, patients will sometimes have just recurrent skin involvement, pleural effusions, or bone disease. Measurable disease is not a requirement for enrollment on the study.
- For patients who have only non-measurable disease, unequivocal progression or response will be defined after consideration if the increase in overall disease burden based on the change in non-measurable disease is comparable in magnitude to the increase that would be required to declare PD or tumor response for measurable disease. Complete response will be defined as disappearance of non-measurable disease.
- Clinical and radiological assessments will be performed every 8 weeks (+- 7 days) while on treatment and patients will be followed for up to 2 years after completion of treatment.

6.3 Secondary Endpoints

- Overall response rate (ORR, defined as Complete Response (CR) + Partial Response (PR)), and Clinical Benefit Rate (CBR, defined as CR + PR + Stable Disease (SD)) in patients with newly recurrent IBC treated with nivolumab and ipilimumab
- Overall survival defined as time in months from the date of first study treatment to the date of death.
- The number, frequency, and severity of adverse events will be collected from the time of consent until 12 weeks after study treatment to evaluate safety of nivolumab and ipilimumab in patients with IBC. Adverse events will follow National Cancer Institute Common Terminology Criteria for Adverse Events (CTCAE) version 4.03

6.4 Definitions

Evaluable for toxicity. All patients will be evaluable for toxicity from the time of their first treatment with nivolumab and or ipilimumab.

Evaluable for objective response. Only those patients who have measurable disease present at baseline, have received at least one dose of therapy, and have had their disease re-evaluated will be considered evaluable for response. These patients will have their response classified according to the definitions stated below.

Evaluable non-target disease response. Patients who have lesions present at baseline that are evaluable but do not meet the definitions of measurable disease, have received at least one dose of therapy, and have had their disease re-evaluated will be considered evaluable for non-target disease. The response assessment is based on the presence, absence, or unequivocal progression of the lesions.

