6.7 Evaluable patients

All patients who receive at least one dose of nivolumab/ipilimumab combination will be evaluable for the secondary endpoints of safety and overall survival (OS). All patients who have at least one on-study scan after baseline will be evaluable for the primary endpoint of PFS, and secondary endpoints of ORR and CBR.

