10.3 Data Analyses Plans

Response rates and 95% confidence intervals will be calculated using exact binomial probability distributions. Progression-free survival and overall survival will be analyzed using Kaplan-Meier curves. Adverse events will be summarized descriptively using frequencies and percentages. Statistics will be given on type, severity, frequency and attribution of adverse events. Sample size considerations are described above.

An intention to treat analysis will be done. In a single group Phase II study, intention to treat means that all patients who are evaluated and registered for the study are followed and analyzed regardless of (a) whether they were subsequently found to be protocol ineligible and (b) the amount of study treatment (nivolumab/ipilimumab) they received. To calculate progression-free and overall survival in patients who received nivolumab/ipilimumab, times will be taken from the time of study registration. This definition parallels the definition of intention to treat in randomized clinical trials.

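### Sections 6.4, 6.7 and 10.3 give different denominators for ORR and CBR, and no rule counts patients without a post-baseline assessment as non-responders

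*Combined protocol and SAP*

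**What the plan says.** Section 6.4 has two response categories. A patient is evaluable for objective response under this rule: "Only those patients who have measurable disease present at baseline, have received at least one dose of therapy, and have had their disease re-evaluated". Patients with only non-measurable lesions fall in a second category, which also requires that they "have had their disease re-evaluated will be considered evaluable for non-target disease". The section does not say whether the two categories are pooled for ORR.

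Section 6.7 uses one set for three endpoints: patients with "at least one on-study scan after baseline will be evaluable for the primary endpoint of PFS, and secondary endpoints of ORR and CBR". It has no measurability condition.

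Section 10.3 defines intention to treat so that "all patients who are evaluated and registered for the study are followed and analyzed regardless of" eligibility or amount of treatment. On the response analysis it says: "Response rates and 95% confidence intervals will be calculated using exact binomial probability distributions". It names no denominator for them.

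Section 6.2 states: "Measurable disease is not a requirement for enrollment on the study". It notes that measurable disease is often absent in IBC and describes how response is judged without it. Section 6.3 gives "Clinical Benefit Rate (CBR, defined as CR + PR + Stable Disease (SD)) in patients with newly recurrent IBC treated with nivolumab and ipilimumab", which points to treated patients and carries no scan condition.

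Section 4.7 continues imaging every 8 weeks for patients who stop for unacceptable toxicity without progression, and counts a response found then.

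**The concern.** A patient with no assessment after baseline has no recorded CR, PR or SD. Counted as a non-responder, that patient lowers both rates; left out, the patient raises them. Those missing any assessment include early deaths and patients who deteriorate clinically without a scan, so leaving them out favours the treatment. A single-arm trial of 29 has no control group in which the same exclusion could offset this.

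Because several denominators can be defended from the text and no order of precedence is given, the reported rate could also be chosen after the data are known. This matters because the study summary lists ORR among the primary as well as the secondary objectives (sections 2.2 and 10.1.2 list it as secondary only), and section 1.4 plans to correlate ORR with biomarkers.

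**Working it through.** **1. The plan's own figures.** Section 10.2 treats 15 patients, stops if 7 or fewer are progression-free at 3 months, otherwise adds 14, and rejects the null if at least 11 of 29 are progression-free at 6 months. Progression-free proportions at 3 and 6 months are 0.50 and 0.25 (null) or 0.7071 and 0.50 (alternative). Let X ~ Bin(15, S3), Y given X ~ Bin(X, S6/S3) and Z ~ Bin(14, S6); reject if X ≥ 8 and Y + Z ≥ 11.

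- Early stopping: 50.0% under the null and 4.37% under the alternative (stated 50% and 4.4%).
- Type I error: 0.0701 (stated 7%).
- Power: 0.901 (stated 90%).

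These reproduce. ORR and CBR do not appear in the calculation, and the plan gives no target, assumed rate or precision for either.

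**2. The rules side by side.**

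| Rule | Measurable disease needed | Post-baseline condition |
|---|---|---|
| 6.4, objective response | yes | re-evaluated |
| 6.4, non-target disease | no | re-evaluated |
| 6.7, ORR and CBR | no | at least one scan |
| 10.3, intention to treat | no | none |

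**3. Effect of the assessment condition.** Let r be the number with the outcome (CR + PR for ORR; CR + PR + SD for CBR) and k the number of the 29 with no post-baseline assessment. None of the k can be among the r. The rate moves from r/29 to r/(29-k), a factor of 29/(29-k) that does not depend on r.

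Neither k nor r is in the documents. The table assumes k = 0 to 7, 5 responders and 12 patients with clinical benefit; intervals are exact (Clopper-Pearson) 95%.

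| k | Factor | ORR, r = 5 | CBR, r = 12 |
|---|---|---|---|
| 0 | 1.00 | 5/29 = 17.2% (5.8-35.8) | 12/29 = 41.4% (23.5-61.1) |
| 1 | 1.04 | 5/28 = 17.9% (6.1-36.9) | 12/28 = 42.9% (24.5-62.8) |
| 3 | 1.12 | 5/26 = 19.2% (6.6-39.4) | 12/26 = 46.2% (26.6-66.6) |
| 5 | 1.21 | 5/24 = 20.8% (7.1-42.2) | 12/24 = 50.0% (29.1-70.9) |
| 7 | 1.32 | 5/22 = 22.7% (7.8-45.4) | 12/22 = 54.5% (32.2-75.6) |

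**4. Effect of the measurable-disease condition.** Suppose 6.4 is read as leaving out m patients with only non-measurable disease, of whom s respond. The rate becomes (r-s)/(29-m). This exceeds r/29 if s/m is below r/29 and falls short of it if s/m is above. The documents give neither s nor m, so the direction is unknown.

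**The case against.** The best defence is that 10.3 governs the analysis and that 6.4 and 6.7 only describe whose response can be classified. Patients who stop early for toxicity without progression are still imaged under 4.7, and a later response counts. Section 6.4 asks for re-evaluation rather than a scan, and footnote 3 of the schedule lets tumour assessment use clinical criteria, so a patient who deteriorates clinically may qualify there. Patients with non-measurable disease have their own category.

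Much of this stands. Stopping treatment does not by itself remove a patient; what matters is having no later assessment. Only 6.7 plainly requires a scan. But 6.7 names ORR and CBR directly, 10.3 does not say that it overrides 6.7, and no section scores an unassessed patient as a non-responder.

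Three stronger readings are tempting and are not supported:

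- **That the size of k follows from the design assumptions.** Under the exponential medians of 3 and 6 months, 1 - 0.5^((84/30.4375)/3) = 47% and 1 - 0.5^((84/30.4375)/6) = 27% have a PFS event by day 84. These are PFS events, not unscanned patients. Progression seen on a scan leaves the patient evaluable. The date of the first scan is itself unsettled: 12 weeks in 6.1 and the schedule, 8 weeks in 6.2. Those passages must be reconciled.
- **That CBR is hit harder than ORR.** Both rise by the same factor. At k = 7, 22.7/17.2 and 54.5/41.4 are both 1.32; only the gap in percentage points differs, because the assumed CBR starts higher.
- **That 6.4 removes patients with non-measurable disease and so inflates the rates further.** It puts them in a separate category without saying whether the two are pooled, and step 4 shows that the direction of any effect is unknown.

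**Conclusion.** Wrong as written. The plan has no single denominator for ORR and CBR and no non-responder rule, and 6.7 taken literally biases both rates upwards whenever at least one patient is unassessed and at least one has the outcome. The direction is certain for the assessment condition; the size is not. For an assumed k of 1 to 7 out of 29 the factor is 1.04 to 1.32, and at k = 0 it is 1. This takes all 29 as treated and changes nothing but the assessment condition. The measurable-disease wording in 6.4 is a further inconsistency with 6.2 and 6.7, of unknown direction.

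A reader might infer that the trial's main conclusion is at risk. On these endpoints it is not: ORR and CBR play no part in the 15- and 29-patient rules, so the stated 90% power and 7% type I error are unaffected. The same sentence of 6.7 also names PFS, against the at-least-one-dose set in 6.2. That is a separate question, and nothing here depends on it.

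**What to change.** In 6.4, 6.7 and 10.3, state one primary denominator for ORR and CBR that does not depend on a post-baseline scan and that includes patients with non-measurable disease. Two choices fit the existing text: all patients who received at least one dose, which matches 6.2 and 6.3, or all registered patients, which matches 10.3. If the second is chosen, note that 4.9 allows untreated patients to be replaced, so the number registered may exceed 29.

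State that a patient with no post-baseline assessment, whatever the reason, counts as a non-responder without clinical benefit. Keep the 6.4 and 6.7 evaluable sets as labelled supportive analyses, and report the number unassessed with reasons.

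The cost is wording in three sections and no new data. The reported rates may be somewhat lower than on the evaluable sets.

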6.5 Disease parameters

Measurable disease. Measurable lesions are defined as those that can be accurately measured in at least one dimension (longest diameter to be recorded) as ≥ 20 mm (≥ 2 cm) by chest x-ray or as ≥ 10 mm (≥ 1 cm) with CT scan, MRI, or calipers by clinical exam (such measurements must be clearly documented). All tumor measurements must be recorded in millimeters (or decimal fractions of centimeters).

Malignant lymph nodes. To be considered pathologically enlarged and measurable, a lymph node must be ≥ 15 mm (≥ 1.5 cm) in short axis when assessed by CT scan (CT scan slice thickness recommended to be no greater than 5 mm [0.5 cm]). At baseline and in follow-up, only the short axis will be measured and followed.

Non-measurable disease. All other lesions (or sites of disease), including small lesions (longest diameter <10 mm [<1 cm] or pathological lymph nodes with ≥ 10 to <15 mm [≥ 1 to <1.5 cm] short axis), are considered non-measurable disease. Bone lesions, leptomeningeal disease, ascites, pleural/pericardial effusions, lymphangitis cutis/pulmonitis, inflammatory breast disease, and abdominal masses (not followed by CT or MRI), are considered as non-measurable.

Note: Cystic lesions that meet the criteria for radiographically defined simple cysts should not be considered as malignant lesions (neither measurable nor non-measurable) since they are, by definition, simple cysts.

'Cystic lesions' thought to represent cystic metastases can be considered as measurable lesions, if they meet the definition of measurability described above. However, if non-cystic lesions are present in the same patient, these are preferred for selection as target lesions.

NU Study Number: NU 16B07
Other Study Number: CA 209-782

Target lesions. All measurable lesions up to a maximum of 2 lesions per organ and 5 lesions in total, representative of all involved organs, should be identified as target lesions and recorded and measured at baseline. Target lesions should be selected on the basis of their size (lesions with the longest diameter), be representative of all involved organs, but in addition should be those that lend themselves to reproducible repeated measurements. It may be the case that, on occasion, the largest lesion does not lend itself to reproducible measurement in which circumstance the next largest lesion which can be measured reproducibly should be selected. A sum of the diameters (longest for non-nodal lesions, short axis for nodal lesions) for all target lesions will be calculated and reported as the baseline sum diameters. If lymph nodes are to be included in the sum, then only the short axis is added into the sum. The baseline sum diameters will be used as reference to further characterize any objective tumor regression in the measurable dimension of the disease.

Non-target lesions. All other lesions (or sites of disease) including any measurable lesions over and above the 5 target lesions should be identified as non-target lesions and should also be recorded at baseline. Measurements of these lesions are not required, but the presence, absence, or in rare cases unequivocal progression of each should be noted throughout follow-up.

6.6 Response Criteria

6.6.1 Evaluation of target lesions

Complete Response (CR): Disappearance of all target lesions. Any pathological lymph nodes (whether target or non-target) must have reduction in short axis to <10mm.

Partial Response (PR): At least a 30% decrease in the sum of the diameters of target lesions, taking as reference the baseline sum diameters.

Progressive Disease (PD): At least a 20% increase in the sum of the diameters of target lesions, taking as reference the smallest sum on study (this includes the baseline sum if that is the smallest on study). In addition to the relative increase of 20%, the sum must also demonstrate an absolute increase of at least 5 mm (0.5 cm). (Note: the appearance of one or more new lesions is also considered progressions).

Stable Disease (SD): Neither sufficient shrinkage to qualify for PR nor sufficient increase to qualify for PD, taking as reference the smallest sum diameters while on study.

6.6.2 Evaluation of Non-Target Lesion

Complete Response (CR): Disappearance of all non-target lesions and normalization of tumor marker level. All lymph nodes must be non-pathological in size (<10 mm [<1 cm] short axis).

Non-CR/Non-PD: Persistence of one or more non-target lesion(s) and/or maintenance of tumor marker level above the normal limits.

Progressive Disease (PD): Appearance of one or more new lesions and/or unequivocal progression of existing non-target lesions. Unequivocal progression should not normally trump target lesion status. It must be representative of overall disease status change, not a single lesion increase.

Although a clear progression of "non-target" lesions only is exceptional, the opinion of the treating physician should prevail in such circumstances, and the progression status should be confirmed at a later time by the review panel (or Principal Investigator).

NU Study Number: NU 16B07
Other Study Number: CA 209-782

6.6.3 Evaluation of best overall response

The best overall response is the best response recorded from the start of the treatment until disease progression/recurrence (taking as reference for progressive disease the smallest measurements recorded since the treatment started). The patient's best response assignment will depend on the achievement of both measurement and confirmation criteria. Responses will be assessed using CT scans or magnetic resonance imaging according to standard RECIST 1.1 criteria in order to assess disease progression. These criteria will also allow for patients who experience an initial disease flare, and as some patients who will have a delayed response may experience an initial disease flare, we will allow patients to continue receiving nivolumab beyond progression (see section 4.4).

6.6.4 Duration of response

Duration of overall response: The duration of overall response is measured from the time measurement criteria are met for CR or PR (whichever is first recorded) until the first date that recurrent or progressive disease is objectively documented (taking as reference for progressive disease the smallest measurements recorded since the treatment started).

The duration of overall CR is measured from the time measurement criteria are first met for CR until the first date that progressive disease is objectively documented.

Duration of stable disease: Stable disease is measured from the start of the treatment until the criteria for progression are met, taking as reference the smallest measurements recorded since the treatment started, including the baseline measurements.

6.7 Evaluable patients

All patients who receive at least one dose of nivolumab/ipilimumab combination will be evaluable for the secondary endpoints of safety and overall survival (OS). All patients who have at least one on-study scan after baseline will be evaluable for the primary endpoint of PFS, and secondary endpoints of ORR and CBR.

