2.0 OBJECTIVES & ENDPOINTS

2.1 Primary Objective & Endpoint

To determine progression free survival (PFS) in patients with newly recurrent HER2 negative IBC treated with nivolumab and ipilimumab according to Response Evaluation Criteria in Solid Tumors (RECIST) v 1.1.⁴⁶

The time in months from start of treatment to progression or death will be measured for all patients who receive at least one dose of study drug. Patients will be followed up to 2 years after completion of treatment.

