10.2 Sample Size and Accrual

We previously identified 44 patients who were included in a retrospective study of the prognostic significance of HER2 status in IBC. These patients had both HER2 negative and HER2 positive disease, developed metastases, and experienced a disease progression. The median time from the first progression of their metastatic disease to the second progression event or death was approximately 3 months. These patients will be considered our historical control group.

Nivolumab ipilimumab combination will be considered of interest for further study if the median PFS time is increased to at least 6 months. We will test the null hypothesis that median PFS is at most 3 months versus the alternative that it is at least 6 months. The null corresponds to 25% PFS at 6 months under the exponential distribution of PFS versus an alternative 6 month PFS rate of 50%. The null corresponds to 50% PFS at 3 months and the alternative corresponds to 70.71% PFS at 3 months under the same conditions.

We will initially recruit and treat 15 patients. If 7 or fewer initial cohort patients are progression free at 3 months the study will be terminated for lack of efficacy. If at least 8/15 are progression-free at 3 months then we will recruit an additional 14 patients for a total of 29.

The patients free of progression at 3 months from the initial cohort will remain on study until either progression or 6 months evaluation. Second cohort patients will be evaluated at 6 months only. If at least 11/29 patients are progression free at 6 months the null hypothesis will be rejected.

The chance of early study termination (3 months follow up with 15 patients) is 50% under the null and 4.4% under the alternative. Study power is 90% with overall type I error of 7%. The design follows: Early stopping designs based on progression-free survival at an early time point in the initial cohort.⁴⁹

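### Primary PFS has conflicting analysis populations (6.7 and 10.3 against 2.1 and 6.2) and two starting dates (10.3 against 2.1 and 6.2), and 10.2 does not say which of them feeds the decision rule

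*Combined protocol and SAP*

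**What the plan says.** **Population.**
- Section 2.1 measures the time "from start of treatment to progression or death will be measured for all patients who receive at least one dose of study drug".
- Section 6.2 agrees: "All patients who receive at least one dose of nivolumab/ipilimumab combination will be included in the primary analyses of PFS".
- Section 6.7 first uses at least one dose to define who is evaluable for safety and OS. For PFS, ORR and CBR it then changes the condition: "All patients who have at least one on-study scan after baseline will be evaluable for the primary endpoint of PFS".
- Section 10.3 describes an intention-to-treat analysis in which "all patients who are evaluated and registered for the study are followed and analyzed", whatever amount of treatment they received.
- Section 4.9 allows consented but untreated patients to be replaced.

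**Clock.**
- Section 6.2 measures PFS "from the date of first study treatment to the date of disease progression or death from any cause, whichever comes first", and 2.1 also starts at treatment.
- Section 10.3, in a sentence limited to patients who received the study drugs, says "times will be taken from the time of study registration".
- Footnote 12 of section 5.0 allows up to 14 days between registration and first treatment.

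**Decision rule.** Section 10.2 says "We will initially recruit and treat 15 patients" and requires at least 8 of them to be progression-free at 3 months. After a further 14 patients, "If at least 11/29 patients are progression free at 6 months the null hypothesis will be rejected". It names neither an analysis set nor the date from which 3 and 6 months are counted.

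**Scan timing.** Section 5.0 (footnote 3) and section 6.1 put the first post-baseline assessment at 12 weeks. The last bullet of 6.2 has assessments every 8 weeks on treatment.

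**The concern.** A treated patient who dies before the first scan is a PFS event under 6.2 and is absent under 6.7, so membership of the 6.7 set depends on the outcome being measured. Such deaths are plausible: inclusion criterion 3.1.8 admits ECOG 2 or 3 when the decline is due to disease burden. The two origins also give different PFS times for the same patient.

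Two things are at stake. The reported Kaplan-Meier estimate depends on which section the analyst follows, and that choice could be made after the data are seen. The error rates of the 8/15 and 11/29 rule also depend on a denominator and a landmark origin that 10.2 leaves unstated.

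**Working it through.** **1. Reproduce the design.** Inputs from 10.2: exponential PFS with median 3 months (null) or 6 months (alternative), so the 3-month rate p3 is 0.50 or 0.7071 and the 6-month rate p6 is 0.25 or 0.50. Let X ~ Bin(15, p3) and continue if X ≥ 8. First-cohort successes at 6 months are Y given X ~ Bin(X, p6/p3), and the second cohort contributes Z ~ Bin(14, p6). Reject if Y + Z ≥ 11.

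| Quantity | Stated | Exact |
|---|---|---|
| Type I error | 7% | 7.01% |
| Power | 90% | 90.1% |
| Early stop, null | 50% | 50.0% |
| Early stop, alternative | 4.4% | 4.4% |

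The stated figures therefore hold when every patient counts and time runs from the date at which the assumed hazard starts.

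**2. How many failures could precede a scan.** Under the null, the share with an event by time t (months) is 1 − 0.5^(t/3).
- Week 8 (56/30.44 = 1.84 months): about 35%.
- Week 12 (84/30.44 = 2.76 months): about 47%.

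These are ceilings on the excluded group, since many of these patients would still be scanned.

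**3. Bias in the estimate under 6.7.** Let f be the share of treated patients who fail with no post-baseline scan (assumed; not in the documents). The 6-month rate in the 6.7 set is 0.25/(1 − f).

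| f | Null 6-month PFS reads | Share of pre-week-12 null failures unscanned (f/0.471) |
|---|---|---|
| 5% | 0.25/0.95 = 26.3% | 11% |
| 10% | 0.25/0.90 = 27.8% | 21% |
| 20% | 0.25/0.80 = 31.3% | 42% |

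The last column shows why 20% is an extreme case.

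**4. Decision rule if 15 and then 29 scanned patients are counted.** Replace p3 and p6 by 0.50/(1 − f) and 0.25/(1 − f) in step 1. Type I error becomes 9.8%, 13.8% or 26.2% for f = 5%, 10% or 20%.

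**5. Decision rule if landmarks run from registration.** Keep all treated patients, with the null hazard starting at first dose. A gap of g months gives p3 = 0.5^((3 − g)/3) and p6 = 0.5^((6 − g)/3).

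| Gap | p3 | p6 | Type I error |
|---|---|---|---|
| 3 days | 0.512 | 0.256 | 8.2% |
| 7 days | 0.527 | 0.264 | 10.0% |
| 14 days (0.46 month, maximum) | 0.556 | 0.278 | 13.8% |

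**6. Does counting only deaths cure the bias?** Simulation at f = 10%: 29 treated patients, null exponential PFS, unscanned failures dated at their true time, other progression dated at the next 12-weekly scan, Kaplan-Meier read at 6 months. The estimate is about 28% in all treated patients and about 31% in the 6.7 set. If half of the unscanned failures are deaths (assumed) and the living half are censored, it is about 29.5%. Roughly half of the gap remains.

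**The case against.** - **6.7 does not say only.** Section 6.4 does use that word when it restricts a set. But 6.7 moves from at least one dose (safety, OS) to at least one scan (PFS, ORR, CBR), and that contrast has no purpose unless the scan condition restricts the set. The restriction is an inference, and a strong one.
- **10.3 is less clear-cut than it looks.** Its timing sentence covers patients who received treatment, and 4.9 replaces untreated patients, so 10.3 can be read as close to all treated for PFS. This stands and softens the population conflict with 10.3. It does not remove the clock conflict or the conflict with 6.7.
- **The excluded group may be small.** Patients who stop for toxicity without progression are imaged every 8 weeks (4.7). Section 6.1 continues assessments when dosing is interrupted, and 6.2's 8-weekly schedule would bring the first scan forward. This stands: f has no source in the documents, so the size of the bias is uncertain.
- **Choosing first dose is partly preference.** It is, but 2.1 and 6.2 already agree on it.

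A reader might infer that the trial's real type I error is 14% or 26%. The documents do not support that: 10.2 adopts neither the scanned set nor the registration date, and its reference to treating the first 15 points towards treated patients. The opposite inference, that the rule is safe in any case, is not supported either. Step 5 shows that the clock alone moves the error rate with every treated patient counted.

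**Conclusion.** Wrong as written, and should be fixed. The current text gives incompatible definitions of who is in the primary PFS analysis and when the clock starts. The sample-size figures are correct for all treated patients timed from first dose; the defect is that the plan does not tie the rule to that set and that clock. Under 6.7 the estimate is biased upward by 1.3, 2.8 or 6.3 points at 6 months under the null for f = 5%, 10% or 20% (26.3, 27.8 or 31.3 less 25). The type I errors in steps 4 and 5 are conditional: they apply only if the scanned set or the registration clock is used for the rule. They also rest on an assumed f, or on an assumed gap within the 14-day maximum. Confidence is high for the contradiction and low for the size of the bias.

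**What to change.** - **6.7:** remove the scan requirement for PFS. State that all patients with at least one dose are in the primary PFS analysis and that death before any scan is an event. State how a living patient with clinical progression but no scan is classified, consistent with footnote 3 of section 5.0, which brings clinical criteria into tumor assessment alongside RECIST. Censoring such patients would leave part of the bias. Censor other event-free patients without a scan at a stated date.
- **10.3:** use the same population and first dose as the origin, as in 2.1 and 6.2. A registration-based analysis can be kept as a labelled sensitivity analysis.
- **10.2:** state that 8/15 and 11/29 are counted on all treated patients, with 3 and 6 months measured from first dose.
- **5.0, 6.1 and 6.2:** reconcile the 12-week and 8-week assessment intervals, since they determine who can fail before a scan.

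The population and clock changes need wording only: no added patients or visits, because footnote 15 of section 5.0 already follows patients off treatment for survival and progression for up to 2 years. The downside is that reported PFS may be slightly less favorable.
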